Key safety assessments	Safety and tolerability of OAV101 treatment includes evaluation of AEs, laboratory data, vital signs, and ECG and echocardiogram.
Data analysis	The primary endpoints include:
	Incidence and severity of treatment emergent AEs and SAEs
	2. Incidence of adverse events of special interest (AESI).
	3. Change from baseline in vital signs, clinical laboratory, and procedure (eg ECG, echocardiogram) results
	Incidence and severity for treatment emergent AEs and SAEs as well as important identified and important potential risks will be summarized overall in the safety set. The number and proportion of participants reporting a treatment emergent AE or SAE, including investigator and Sponsor causalities will be reported. Summaries will also be provided by MedDRA System Organ Class and Preferred Term.
	Changes from baseline in vital signs, and clinical laboratory, and procedure (eg ECG, echocardiogram) results will be summarized descriptively overall in the safety set. Mean, standard deviation, median, minimum, and maximum will be presented. For each applicable timepoint, only participants with a baseline and a measurement for that timepoint will be included in the summary.
	The number and proportion of patients achieving each Developmental Motor Milestone will be presented.
	An interim analysis may be performed once the last participant reaches the 6 and 12-month time point and will include all available data up until that data cut-off.
	There is no formal sample size calculation performed for this study. The primary objective is to evaluate descriptively the safety and tolerability of IV OAV101 over a 18 month post infusion period in participants with SMA weighing equal or less than 17kg. No hypothesis testing will be performed.

Novartis	Confidential	Page 17 of 66
Clinical Trial Protocol (Version No. 01)		Protocol No. COAV101A1IC01

	The sample size is based on recruitment estimatives and clinical drug availability. Based on this assumption, it is anticipated that approximately 15 participants will be enrolled in this study. From a medical perspective, this number is considered reasonable to provide descriptive safety information. If the true incidence rate of an AE is 14%, then the probability of seeing at least one AE with a sample size of 15 participants is approximately 90%.
Key words	Spinal muscular atrophy, Zolgensma, OAV101, AVXS-101, gene therapy

1 Introduction

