The chronic use of corticosteroids may be associated with hypothalamic-pituitary-adrenal axis suppression, Cushing's syndrome and hyperglycemia which can be mitigate with adequate tapering. Increased susceptibility to new infections or exacerbation and dissemination of latent infections, as well as elevated blood pressure, salt and water retention, hypokalemia, and gastrointestinal perforation have been reported. Risks will be mitigated by close monitoring, and implementation of standard prophylaxis and tapering protocol as detailed in Section 6.2

Risk of phlebotomy (maximum volume over what period of time)

European Medicines Agency (EMA) Guidelines for Drawing Blood and Best practices in Phlebotomy in pediatric participants will be followed.

Drug-drug interaction

OAV101 is a gene replacement therapy product for one-time administration, which delivers a transgene construct expressing the SMN protein. Drug-drug interactions are not expected with OAV101.

In summary, clinical data strongly suggest OAV101 is safe and well tolerated with an acceptable benefit/risk profile when administered to participants with SMA with 2 or 3 SMN2 copies or a clinical diagnosis of SMA.

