12.4.2 Statistical model, hypothesis, and method of analysis

No statistical hypothesis testing will be performed.

Treatment-emergent AEs are defined as any event that begins or worsens in severity after infusion of OAV101 through to the last study visit. The incidence of TEAEs will be summarized according to MedDRA as follows: overall by SOC and PT, overall, by SOC, PT and severity, suspected treatment-related AEs by SOC and PT, SAEs by SOC and PT.

Adverse events of special interest (AESI) are defined by the important identified risk and important potential risk as presented in the effective Risk Management Plan (RMP). MedDRA search criteria to retrieve AEs indicative of these risks are updated on a regular basis at the

OAV101 program level. The incidence of treatment emergent AESIs will be summarized. Descriptive summary statistics for the change from baseline in cardiac safety assessments, clinical laboratory measurements, and vital signs will be summarized descriptively by visit/timepoint. Mean, standard deviation, median, minimum, and maximum will be presented. For each applicable visit/timepoint, only participants with a baseline and a measurement for that timepoint will be included in the summary. Categorical cardiac safety assessments, clinical laboratory measurements, and vital signs data will be presented as frequencies and percentages.

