15.1.1 Adverse Events

Adverse Events (AEs) will be coded using MedDRA, Version 25 or later.

Treatment Emergent Adverse Events (TEAEs) are defined as AEs that started or worsened in severity on or after the OAV101 dosing through the last study visit.

Adverse events of special interest (AESI) are defined by the important identified risk an important potential risk as presented in the effective Risk Management Plan (RMP). The AESI will be summarized following the classification presented in Table 2.

Document: Document path and title

Template No.: RWI_TP_BIOS0013 Revision 2 Reference: RWI_WI_BIOS0015

Table 2: Adverse events of special interest classification

AESI	Search methodology (MedDRA version 25.0 or later) [MedDRA
	Code]
Hepatotoxicity	Hepatic disorders SMQ (Broad) [20000005]
Transient thrombocytopenia	Haemorrhages SMQ (Broad) [20000038]
	Haematopoietic thrombocytopenia SMQ (Broad) [20000031]
	HLT: Platelet disorders NEC [10035533]
Thrombotic microangiopathy	PTs:
	Thrombotic microangiopathy [10043645]
	Haemolytic uraemic syndrome [10018932]
	Atypical haemolytic uraemic syndrome [10079840]
Cardiac events	Cardiomyopathy SMQ (Broad) [20000150]
	Ischaemic heart disease SMQ (Broad) [20000043]
	Cardiac arrhythmias SMQ (Broad) [20000049]
	Embolic and thrombotic events SMQ (Broad) [20000081]
	Myocardial infarction SMQ (Broad) [20000047]
	Cardiac failure SMQ (Broad) [20000004]
	Hypertension SMQ (Broad) [20000147]
Sensory Abnormalities	PTs:
Suggestive of Ganglionopathy	Akinaesthesia [10051224]
	Allodynia [10053552]
	Anaesthesia [10002091]
	Anaesthesia dolorosa [10054878]
	Areflexia [10003084]
	Burning feet syndrome [10070237]
	Burning sensation [10006784]
	Central pain syndrome [10064012]

Document: Document path and title

Template No.: RWI_TP_BIOS0013 Revision 2 Reference: RWI_WI_BIOS0015

AESI	Search methodology (MedDRA version 25.0 or later) [MedDRA
	Code]
	Complex regional pain syndrome [10064332]
	Decreased vibratory sense [10067502]
	Discomfort [10013082]
	Dysaesthesia [10013886]
	Formication [10017062]
	Hyperaesthesia [10020568]
	Hyperpathia [10065952]
	Hypoaesthesia [10020937]
	Hyporeflexia [10021089]
	Hyporesponsive to stimuli [10071552]
	Intercostal neuralgia [10049949]
	Joint position sense decreased [10081223]
	Loss of proprioception [10057332]
	Nerve conduction studies abnormal [10029175]
	Nerve stimulation test abnormal [10029192]
	Neuralgia [10029223]
	Neuritis [10029240]
	Neurological symptom [10060860]
	Neuromuscular pain [10074313]

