	Notalgia paraesthetica [10072643]
	Pain [10033371]
	Pain threshold decreased [10066956]
	Paradoxical pain [10067055]
	Paraesthesia [10033775]
	Peripheral nervous system function test abnormal [10034591]
	Peripheral sensorimotor neuropathy [10056673]
	Peripheral sensory neuropathy [10034620]
	Radicular pain [10059604]

Document: Document path and title

Template No.: RWI_TP_BIOS0013 Revision 2 Reference: RWI_WI_BIOS0015

AESI	Search methodology (MedDRA version 25.0 or later) [MedDRA	
	Code]	
	Reflex test abnormal [10068273]	
	Reflexes abnormal [10038254]	
	Reversed hot-cold sensation [10073738]	
	Sensorimotor disorder [10062162]	
	Sensory disturbance [10040026]	
	Sensory ganglionitis [10066196]	
	Sensory integrative dysfunction [10048871]	
	Sensory level abnormal [10061567]	
	Sensory loss [10040030]	
	Skin burning sensation [10054786]	
	Slow response to stimuli [10041045]	
	Synaesthesia [10078814]	
	Temperature perception test decreased [10068015]	
	Tenderness [10043224]	
	Thermoanaesthesia [10068010]	
	Thermohypoaesthesia [10068009]	
	Tinel's sign [10052492]	
	Trichodynia [10079852]	
	Unresponsive to stimuli [10045555]	
	Vibratory sense increased [10068327]	

AESI: Adverse event of special interest; HLT: High Level Terms; PT: Preferred Terms; SMQ: Standardized MedDRA Queries

See Appendix 2 for handling of partial dates for AEs. In the case where it is not possible to define an AE as treatment emergent or not, the AE will be classified by the worst case; i.e. treatment emergent.

Document: Document path and title

Template No.: RWI_TP_BIOS0013 Revision 2 Reference: RWI_WI_BIOS0015

Page 23 of 45

The incidence of TEAEs and AESIs will be summarized. Descriptive summary statistics for the change from baseline in cardiac safety assessments (ECG, Echocardiogram, troponin), clinical laboratory measurements (including hematology and liver function assessments), and vital signs will be summarized descriptively by visit/timepoint. A summary of all laboratorial assessments (including scheduled and unscheduled visits) will be summarized separately. Mean, standard deviation, median, minimum, and maximum will be presented for continuous variables. Categorical data will be presented as frequencies and percentages. For each applicable visit/timepoint, only participants with a baseline and a measurement for that timepoint will be included in the summary.

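### SAP Table 2 assigns AESI categories by coded term alone, so three category incidences can consist of events that do not show the named risk; a risk-specific count should be prespecified beside them

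*SAP*

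**What the plan says.** The data analysis part of the protocol summary lists "Incidence of adverse events of special interest (AESI") as the second primary endpoint. Protocol 12.4.2 ties AESIs to the risks in the Risk Management Plan, says that the MedDRA search criteria are maintained at program level, and adds: "The incidence of treatment emergent AESIs will be summarized". Protocol 4.5 and 10.1.1 name five risks: hepatotoxicity, thrombocytopenia, cardiac adverse events, sensory abnormalities suggestive of ganglionopathy, and thrombotic microangiopathy.

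SAP 15.1.1 turns this into a rule: "The AESI will be summarized following the classification presented in Table 2". Three rows of that table matter here.

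- **Transient thrombocytopenia** takes "Haemorrhages SMQ (Broad) [20000038" as well as two platelet-specific searches, "Haematopoietic thrombocytopenia SMQ (Broad) [20000031" and the high-level term for platelet disorders NEC.
- **Cardiac events** takes seven broad SMQs, one of which is "Hypertension SMQ (Broad) [20000147".
- **Sensory abnormalities suggestive of ganglionopathy** is a list of preferred terms that includes "Pain [10033371", Discomfort, Tenderness and Neurological symptom.

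No row requires a platelet, cardiac or sensory finding. The text around the table describes no narrow-versus-broad split and no confirmation step.

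**The concern.** The label on each category names a specific risk, but the events counted under it need not show that risk. A nosebleed in a child with a normal platelet count would enter as thrombocytopenia. A blood-pressure event with a normal ECG, echocardiogram and troponin would enter as cardiac. Pain from any cause would enter as possible ganglionopathy.

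Hypertension is the clearest case. Every child takes a corticosteroid for at least 30 days (protocol 6.1.2 and 6.2). The protocol's own account of corticosteroid risk in section 4.5 says that "elevated blood pressure, salt and water retention, hypokalemia, and gastrointestinal perforation have been reported". Hypertension is not one of the five named risks.

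The study has one arm and about 15 children, so there is no concurrent background rate to set against a category count. One or two non-specific events could be quoted as a rate of thrombocytopenia, cardiac events or suspected ganglionopathy.

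**Working it through.** **The plan's own figure.** Protocol 12.7.1 gives about 90% for seeing at least one event when the true rate is 14% and n = 15. The formula is 1 − (1 − p)^15, and 1 − 0.86^15 = 0.896. The figure reproduces.

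**Same formula for the non-specific terms.** Let b be the probability that a child has at least one adverse event in a category's non-specific terms over the 18 months, with no OAV101 effect. The documents give no value for b, so each row is an assumption.

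| Assumed b | P(at least 1 of 15) | Expected children (15b) |
|---|---|---|
| 2% | 26.1% | 0.30 |
| 5% | 53.7% | 0.75 |
| 10% | 79.4% | 1.5 |
| 20% | 96.5% | 3.0 |

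The 50% point is b = 1 − 0.5^(1/15) = 4.5%.

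**How such a count reads.** One child is 1/15 = 6.7% (exact 95% interval 0.2% to 31.9%). Two are 2/15 = 13.3% (1.7% to 40.5%).

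**When there is also a real effect.** If the risk-specific rate is r and the two kinds of event are independent, the category rate is 1 − (1 − r)(1 − b). With r = 5% and b = 5% this is 1 − 0.95 × 0.95 = 9.75%, about twice the specific rate. The values of r and b are illustrative.

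**What else the plan reports on each risk.**

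- *All AESIs:* SAP 15.1.2 breaks them down by SOC and preferred term, maximum severity and relationship.
- *Thrombocytopenia:* hematology is scheduled at 10 post-infusion visits in protocol Table 8-1 (Weeks 1, 2, 3, 6, 8, 10, 12, 26, 52 and 78). Change from baseline, worst CTCAE grade and shift tables follow. None of these is linked to a bleeding AESI.
- *Cardiac:* SAP 15.3.1 defines a cardiac event as a clinically relevant ECG or echocardiogram finding, and SAP 15.3 reports its frequency and time to onset. A child with a hypertension event and normal ECG and echocardiogram is a cardiac AESI under Table 2 but not a cardiac event under 15.3.1. The report can therefore carry two cardiac counts that differ, and the SAP does not say how to read them together.
- *Sensory:* protocol 8.2.4 requires sensory testing at each visit and eCRF entry of clinically significant abnormal findings. The AESI rule does not use them.

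**The case against.** The strongest reply is that broad searching is deliberate. A safety search should favour sensitivity, the criteria are maintained at program level, and the Risk Management Plan behind them is not available here. Protocol 10.1.1 says that AESIs will be summarised on standardised MedDRA terms, so the SAP does what the protocol asks. A reader might infer that the SAP departs from the protocol by counting what was only meant to be retrieved. The documents do not support that, because protocol 12.4.2 itself calls for the incidence to be summarised.

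Four further parts of the reply also stand.

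- The category count is not the trial's only answer on each risk. The ECG/echocardiogram event, the platelet summaries and the preferred-term, severity and relationship tables all exist. With 15 children, a reader can find the term that drove a row.
- It is tempting to fault the embolic and thrombotic SMQ in the cardiac row as well. Protocol 1.1 reports atrial thrombosis among OAV101-related heart findings in mice, so that search has a rationale and belongs in the cardiac count.
- The probability formula applies to any adverse event in any single-arm study of 15. No hypothesis is tested, so a non-zero count is not a false positive.
- Making a narrow definition primary would lose sensitivity. Hematology is not scheduled at Week 4 or between the later visits, so a bleed could drop out merely because no platelet count was near it. A required examination finding would be a similar filter in children aged 24 months or less at dosing.

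The separate tables do not supply a per-child count, by category, of events that show the risk. Preferred-term rows cannot simply be added, because one child may appear in several. The relationship split may not isolate OAV101 either. Protocol 10.1.1 asks about the study treatment and SAP 14 treats the corticosteroid as secondary study medication, although SAP 15.1.2.1 mentions OAV101 and counts a missing relationship as possibly related.

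**Conclusion.** The point holds as a matter of interpretation. For three of the five categories, the planned incidence can be made up wholly or partly of events that do not show the named risk, and no planned table gives the risk-specific count per child. One such child moves a category by 6.7 percentage points.

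How likely this is depends on an assumed background rate: 26% at 2%, 54% at 5% and 79% at 10%, per category. Those figures show sensitivity to the assumption and are not estimates for this trial. The contents of the SMQs are not in the documents, so the statement about bleeding rests on the title and broad scope of that search. The hypertension SMQ and the four bare sensory terms are named outright.

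A reader might go further and conclude that the AESI endpoint is invalid or that the broad search should be replaced. The documents do not support either. The broad search is a defensible planned incidence that needs a companion line. Sample size, power and error rates are untouched.

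**What to change.** Keep the full Table 2 search as the planned AESI incidence, for sensitivity and comparability with the OAV101 program. Before the analysis, add to SAP 15.1.1 a second count per category: the number of children with at least one risk-specific term.

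- **Thrombocytopenia:** the haematopoietic thrombocytopenia SMQ plus the platelet disorders high-level term. Put the haemorrhage SMQ on its own line, and list the nearest available platelet count for each bleed as information, not as a reason to exclude it.
- **Cardiac:** the six SMQs other than hypertension, with embolic and thrombotic events kept in. Put hypertension on its own line. Show the result next to the SAP 15.3.1 cardiac event, with a per-child reconciliation of the two cardiac counts.
- **Sensory:** the listed terms without Pain, Discomfort, Tenderness and Neurological symptom. Put those four on their own line with any recorded sensory examination finding.

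A child with both kinds of event counts once in each line. The cost is SAP wording and one extra table from data already collected. The downside is that the specific lines will hold small numbers.

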15.1.2 All TEAEs and AESI

Incidence of all TEAEs/AESIs and Serious TEAEs/AESIs will be presented by System Organ Class (SOC) and Preferred Term (PT) and also broken down further by maximum severity and relationship to study medication.

15.1.2.1 Relationship to Study Medication

Relationship, as indicated by the Investigator, is classed as possible related or not possible related TEAEs with a missing relationship to study medication are regarded as possible related to study medication (OAV101). If Patient reports the same AE more than once within that SOC/PT, the AE with the worst-case relationship to study medication is used in the corresponding relationship summaries.

15.1.3 TEAEs Leading to Discontinuation of Study Medication

Not applicable.

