6.6 Additional treatment guidance

6.6.1 Treatment compliance

OAV101 will be administered as a single IV injection. If the dose is not fully completed the site personnel will need to reflect the total volume administered as well as the date and time of administration in the eCRF.

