9.1 Discontinuation and completion

9.1.1 Study treatment discontinuation and study discontinuation

Since this is a single dose study, discontinuation of study treatment is not applicable.

Because the study treatment is a single administration gene therapy, stopping or reversing the study treatment is not possible. Participants who decide they do not wish to participate in the study further should NOT be considered withdrawn from the study UNLESS they withdraw their consent (see 'Withdrawal of Informed Consent' section). Where possible, they should return for the assessments indicated in the Assessment Schedule. If they fail to return for these assessments for unknown reasons, every effort (eg telephone, e-mail, letter) should be made to contact the participant/pre-designated contact as specified in the lost to follow-up section. This contact should preferably be done according to the study visit schedule.

If the participant cannot or is unwilling to attend any visit(s), the site staff should maintain regular telephone contact with the participant, or with a person pre-designated by the participant. This telephone contact should preferably be done according to the study visit schedule.

In the event of study discontinuation, the EOS study should be completed. At a minimum, in abbreviated visits, the following data should be collected at clinic visits or via telephone/email contact:

- New / concomitant treatments/medications
- AEs, including SAEs

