10.1 Definition of adverse events and reporting requirements

10.1.1 Adverse events

An AE is any untoward medical occurrence (eg any unfavorable and unintended sign [including abnormal laboratory findings], symptom or disease) in a clinical investigation participant after providing written informed consent for participation in the study. Therefore, an AE may or may not be temporally or causally associated with the use of a medicinal (investigational) product.

The Investigator has the responsibility for managing the safety of individual participant and identifying AEs.

Novartis qualified medical personnel will be readily available to advise on trial related medical questions or problems.

The occurrence of AEs must be sought by non-directive questioning of the participant at each visit during the study. Adverse events also may be detected when they are volunteered by the participant during or between visits or through physical examination findings, laboratory test findings, or other assessments.

Adverse events must be recorded under the signs, symptoms, or diagnosis associated with them, accompanied by the following information (as far as possible) (if the event is serious refer to Section 10.1.2):

- 1. Severity grade
- mild: usually transient in nature and generally not interfering with normal activities
- moderate: sufficiently discomforting to interfere with normal activities
- severe: prevents normal activities
- 2. Its relationship to the study treatment. If the event is due to lack of efficacy or progression of underlying illness (i.e. progression of the study indication) the assessment of causality will

usually be 'Not suspected.' The rationale for this guidance is that the symptoms of a lack of efficacy or progression of underlying illness are not caused by the trial drug, they happen in spite of its administration and/or both lack of efficacy and progression of underlying disease can only be evaluated meaningfully by an analysis of cohorts, not on a single participant

- 3. Its duration (start and end dates) or if the event is ongoing, an outcome of not recovered/not resolved must be reported
- 4. Whether it constitutes a SAE (see Section 10.1.2 for definition of SAE) and which seriousness criteria have been met
- 5. Action taken regarding with study treatment.

All AEs must be treated appropriately.

6. Its outcome (i.e. recovery status or whether it was fatal)

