12.4.8 Safety endpoints

For all safety analyses, the Safety set will be used.

The overall observation period will be divided into two mutually exclusive segments:

- 1. Pre-treatment period: from day of participant's informed consent to the day before infusion of OAV101
- 2. On-treatment period: from day of infusion of OAV101 through to the last study visit.

Adverse events

Details of the summary of AEs for the primary endpoint are detailed in Section 12.4.

In addition, separate summaries will be provided for death and other significant TEAEs leading to discontinuation.

All AEs, deaths, and SAEs (including those from the pre-treatment period) will be listed and those collected during the pre-treatment period will be flagged.

Vital signs

Details of the summary of AEs for the primary endpoint are detailed in Section 12.4.

12-lead ECG

Details of the summary of 12-lead ECG (cardiac safety assessment) for the primary endpoint are detailed in Section 12.4

- 1. PR, QRS, QT, QTcF, and RR intervals will be obtained from 12-lead ECGs for each participant during the study. ECG data will be read and interpreted (locally).
- 2. Categorical Analysis of QT/QTc interval data based on the number of participants meeting or exceeding predefined limits in terms of absolute QT/QTc intervals or changes from baseline will be presented.

All ECG data will be summarized by visit/timepoint.

Clinical laboratory results

Details of the summary of clinical laboratory results for the primary endpoint are detailed in Section 12.4.

In addition, shift tables using the low/normal/high/ (low and high) classification will be used to compare baseline to the worst on-treatment value.

Grading of laboratory values will be assigned programmatically as per NCI CTCAE version 4.03. The calculation of CTCAE grades will be based on the observed laboratory values only, clinical assessments will not be taken into account.

CTCAE Grade 0 will be assigned for all non-missing values not graded as 1 or higher. Grade 5 will not be used.

For laboratory tests where grades are not defined by CTCAE version 4.03, results will be categorized as low/normal/high based on laboratory normal ranges.

The following listings/summaries will be generated separately for hematology, and biochemistry tests:

• Listing of all laboratory data with values flagged to show the corresponding CTCAE version 4.03 grades if applicable and the classifications relative to the laboratory normal ranges

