4.3 Changes to Analysis from Protocol

Not applicable.

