14. STUDY MEDICATION EXPOSURE

Exposure to study medication will be presented for the FAS.

Document: Document path and title

Template No.: RWI_TP_BIOS0013 Revision 2 Reference: RWI_WI_BIOS0015

Page 19 of 45

For the data analysis OAV101 will be considered as primary study medication and the corticosteroid as secondary study medication.

The date of OAV101 dosing will be taken from eCRF OAV101 infusion form.

The date of first corticosteroid administration will be taken from the eCRF Pre-infusion corticosteroid form. The date of last corticosteroid administration will be taken from the eCRF Prophylactic corticosteroid - Post-infusion details form.

Interruptions, compliance, and dose changes are not considered for duration of exposure and will be summarized separately.

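### SAP 15.1.3 leaves out the protocol's summary of TEAEs leading to discontinuation, and SAP 4.3 declares no change

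*SAP*

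**What the plan says.** Protocol 12.4.8 adds to the primary adverse event tables: "separate summaries will be provided for death and other significant TEAEs leading to discontinuation". It does not say whether discontinuation means of treatment or of the study.

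The SAP plans the death half (15.1.5 and 15.2). For the other half, SAP 15.1.3, "TEAEs Leading to Discontinuation of Study Medication", states only that it does not apply. SAP 4.3, which should record changes from the protocol, reads "Not applicable".

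Protocol 9.1.1 gives the likely reason for the entry: "Since this is a single dose study, discontinuation of study treatment is not applicable".

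Other sections show that the subject is not empty:
- SAP 14: "OAV101 will be considered as primary study medication and the corticosteroid as secondary study medication".
- Protocol 6.6.1: "If the dose is not fully completed the site personnel will need to reflect the total volume administered". Protocol 12.3 also plans to summarise incomplete and interrupted infusions.
- Protocol 10.1.1 lists among the items recorded for each adverse event: "Action taken regarding with study treatment".
- Protocol 12.4.3 and 12.4.7, and SAP 16.1, treat leaving the study for reasons other than death as an intercurrent event.

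**The concern.** The primary objective is the safety and tolerability of IV OAV101 over 18 months. An adverse event that ends a child's participation, cuts the infusion short or permanently stops a required accompanying treatment is among the most direct evidence on tolerability. The protocol promised to show such events separately. The SAP removes that output under a heading limited to study medication, and does not say that anything was removed.

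The final report could then hold one table of TEAEs, one of exposure and one of disposition, with nothing to tell the reader which event led to which discontinuation.

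**Working it through.** **The promise against its delivery.** The comparison covers each reading of discontinuation in Protocol 12.4.8.

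| Reading | Foreseen in the documents? | Covered by Protocol 9.1.1? | Summary of causal TEAEs in the visible SAP? |
|---|---|---|---|
| OAV101 stopped after the single dose | No | Yes | None, and none needed |
| OAV101 infusion not completed | Yes: Protocol 6.6.1 and 12.3 | Not addressed | None |
| Corticosteroid permanently stopped early | Possible: it runs from 24 hours before infusion to at least 30 days, then a taper (Protocol 6.2) | No: the reason given is the single dose | None |
| Child leaves the study | Yes: Protocol 12.4.3 and 12.4.7, SAP 16.1 | No: it concerns study treatment | None |

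The entry in 15.1.3 is right for the first row only. The gap remains under every other reading.

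**Is the corticosteroid study medication?** The protocol glossary defines study treatment broadly, as whatever is given under the required study procedures, and defines treatment discontinuation as a permanent stop of any study drug. Protocol 6.1.2 lists the corticosteroid as an additional study treatment. Protocol 2.1 includes it in the treatment of interest, and SAP 14 labels it secondary study medication. By the SAP's own label, a section on discontinuation of study medication has a subject.

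**What is still reported.**
- All TEAEs by SOC and PT, maximum severity and relationship: SAP 15.1.2.
- Interruptions, adherence and dose changes: SAP 14.
- Withdrawals: SAP 10.
- A listing of every adverse event: Protocol 12.4.8.

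No visible section joins these sources.

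**Arithmetic.** The only statistical figure nearby is in Protocol 12.7.1: the chance of at least one event in 15 children at a true rate of 14%. The check is 1 − (1 − 0.14)^15 = 1 − 0.86^15 = 0.896, which agrees with the stated 90%. The present point does not depend on it.

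One child is 1/15 = 6.7%. The documents give no rate of discontinuation due to adverse events, so the rates below are assumptions. With 1 − (1 − p)^15:
- p = 2%: 1 − 0.98^15 = 26%
- p = 5%: 1 − 0.95^15 = 54%
- p = 10%: 1 − 0.90^15 = 79%

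Over this range, at least one case is anything from fairly unlikely to likely. A row showing none would also inform: for 0 of 15, the exact two-sided 95% upper limit is 1 − 0.025^(1/15) = 21.8%. A missing row gives neither result.

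**The case against.** The strongest defence is Protocol 9.1.1. SAP 15.1.3 concerns study medication, and for OAV101 it repeats the protocol's own position. Since Protocol 12.4.8 names no object, it can be read as discontinuation from the study, and then 15.1.3 does not contradict it. SAP 15.1.2.1 also identifies study medication as OAV101, and the secondary label for the corticosteroid appears only in the exposure section. This stands in part: a reader who infers a flat contradiction about OAV101 goes too far. It does not rescue the plan, because the study-discontinuation summary is also absent and SAP 4.3 is silent.

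A reader might infer that tolerability failures go unreported. The documents do not support that. The events, the interruptions and dose changes, and the withdrawals each have a planned output; only the link is missing.

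A reader might also infer that tables of every infusion interruption and corticosteroid dose change are owed. Protocol 12.4.8 speaks of discontinuation, and a dose change is not one.

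Nor does the length of corticosteroid exposure measure the problem. Counting 1 + 30 + 21 = 52 days assumes how the taper in Table 6-2 ends, and a duration says nothing about how often an adverse event forces a stop.

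Finally, SAP Appendix 3 shows no shells in the public copy, so a suitable listing may exist. If so, 15.1.3 would still need correcting, because it says the opposite.

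**Conclusion.** The point holds in limited form. The visible SAP omits a primary safety output that the protocol promises, without declaring a change. Protocol 9.1.1 justifies the omission for the single OAV101 dose only, not for discontinuation from the study or an early permanent stop of the corticosteroid. What is lost is the connection between an adverse event and the discontinuation it caused.

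The effect is on reporting: each affected child is 6.7% of 15, the number of such children cannot be estimated from the documents, and no sample size, power or test is touched. The conclusion assumes that the unseen table shells contain no such output. It also assumes that the recorded action taken, with the infusion, corticosteroid and completion data, is enough to identify these events. The forms themselves are not in the documents, so that needs checking.

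**What to change.** Reconcile Protocol 9.1.1 and 12.4.8 with SAP 4.3, 14 and 15.1.3, and state what discontinuation refers to. Protocol 6.5, which does not permit interruptions, should be reconciled with 6.6.1 and 12.3, which provide for recording them. This concerns reporting only and implies no view on clinical management.

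Then replace the entry in SAP 15.1.3 with one short SOC and PT summary and one listing of TEAEs leading to discontinuation from the study and, where recorded, to incomplete OAV101 infusion or permanent early stop of the corticosteroid. Use the action-taken item and the infusion, corticosteroid and completion data already collected. Show the table even if it is empty. If the sponsor prefers to leave the summary out, record and justify that in SAP 4.3.

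The cost is a SAP wording change, one small table and one listing. No new data are collected, provided the existing forms identify these events.
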